12.3 Stopping Rule, and Rules for Suspending Accrual

12.3.1 Futility: The study will be stopped if two or fewer of the first 9 patients respond after cycle two, as in section 12.2 above.

12.3.2 Cardiac Toxicity: A composite endpoint of cardiotoxicity will lead to suspension of accrual, at the thresholds noted below: myocardial infarction, new onset atrial fibrillation, cerebrovascular accident, grade 4 hypertension, grade 3 left ventricular dysfunction, or grade 2 or higher heart failure. Events are counted per patient (i.e. a patient with more than one cardiac event counts only once toward this limit.)

If there is sufficient evidence to suggest that the occurrence of any of the components of this composite "toxicity" (occurrence of at least one will constitute a "toxicity") exceeds a frequency of 10% of accrued patients, study accrual will be suspended pending review by the institutional data safety monitoring committee. Further accrual may be undertaken only with approval of that committee. Sufficient evidence will be taken to be any observed ratio associated with a lower 80% one-sided confidence limit that exceeds 0.10.

Operationally, any of the following proportions of accrued patients experiencing cardiac toxicity (as defined above) would yield such a ratio: 2 of the first 8 or fewer patients, 3 of the first 15 or fewer patients, 4 of the first 23 or fewer patients.

If the true probability of toxicity is .05, the probability of stopping after 15 or 23 patients is approximately .08 and .08, respectively. If the true probability of toxicity is .25, the probability of stopping after 15 or 23 patients is approximately .81 and .90, respectively (probabilities of stopping estimated from 5,000 simulations).

12.3.3 Inability to deliver rituximab therapy as per protocol:

If per-protocol rituximab (as per protocol section 7.2) cannot be administered to at least 6 of the first eligible 12 patients for any reason, accrual will be suspended for review by the institutional data safety monitoring committee, before further accrual may proceed.

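### Section 12.3.2 defines cardiac suspension so that 1 of 1 or 1 of 2 patients qualifies, but its list of thresholds begins at two events; the text must say which governs

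*Combined protocol and SAP*

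**What the plan says.** Section 12.3.2 (Cardiac Toxicity) has four relevant parts.

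- **Opening.** "A composite endpoint of cardiotoxicity will lead to suspension of accrual, at the thresholds noted below". Patients, not events, are the unit: "Events are counted per patient".
- **Criterion.** If there is sufficient evidence that the composite "exceeds a frequency of 10% of accrued patients, study accrual will be suspended pending review" by the institutional committee. Sufficient evidence is then defined: "Sufficient evidence will be taken to be any observed ratio associated with a lower 80% one-sided confidence limit that exceeds 0.10". No minimum number of events or patients is attached.
- **List.** The working counts are presented as cases that meet this criterion. There are three entries, and the smallest has two affected patients: "2 of the first 8 or fewer patients, 3 of the first 15 or fewer patients, 4 of the first 23 or fewer patients".
- **Operating characteristics.** "If the true probability of toxicity is .05, the probability of stopping after 15 or 23 patients is approximately .08 and .08, respectively". At a true rate of .25 the corresponding figures are .81 and .90. All four come from 5,000 simulations.

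**The concern.** The criterion covers every observed ratio, while the list covers only ratios with two or more affected patients. If one affected patient in the first one or two already puts the lower limit above 0.10, the definition calls for suspension where the list does not. The site and the committee would then have to choose a reading after seeing the event. The quoted operating characteristics would describe only one of the two readings. The event is not far-fetched: the composite includes new atrial fibrillation and heart failure of grade 2 or higher, and Section 2.1 puts any-grade cardiac failure with carfilzomib at about 6-8%.

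**Working it through.** **Inputs (all from Section 12.3.2).** Reference rate 0.10; one-sided 80% lower limit; one count per patient; printed cut-offs 2 in 8, 3 in 15 and 4 in 23; true rates .05 and .25.

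**Step 1: reproduce the cut-offs.** The exact (Clopper-Pearson) lower limit for x affected of n is the 0.20 quantile of a Beta(x, n − x + 1) distribution. It exceeds 0.10 exactly when P(X ≥ x | n, 0.10) is below 0.20.

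| Observed | Lower 80% limit | Above 0.10? |
|---|---|---|
| 2/8 | 0.1044 | yes |
| 2/9 | 0.0926 | no |
| 3/15 | 0.1041 | yes |
| 3/16 | 0.0975 | no |
| 4/23 | 0.1015 | yes |
| 4/24 | 0.0972 | no |

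All three printed cut-offs are reproduced, so this is evidently the method used. Wilson, Wald, mid-P and Jeffreys limits do not reproduce them.

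**Step 2: apply the same method to one event.** With x = 1 the limit is 1 − 0.80^(1/n):

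- 1/1: 1 − 0.80 = 0.200, above 0.10.
- 1/2: 1 − √0.80 = 0.1056, above 0.10.
- 1/3: 1 − 0.80^(1/3) = 0.0717, not above 0.10.

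The definition therefore implies a further entry, one event in two or fewer patients. The four other intervals also put 1/1 and 1/2 above 0.10, so this does not depend on the choice of interval.

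**Step 3: reproduce the quoted probabilities for the list.** Carry the binomial count forward patient by patient and remove the paths that cross a threshold. At a true rate of .05:

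- By patient 8: P(at least 2 of 8) = .0572.
- Patients 9-15 add .0149, giving .0721.
- Patients 16-23 add .0079, giving .0801.

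At .25 the same recursion gives .6329 + .1726 = .8055 (unrounded .80549, so .805), then + .0954 = .9009. The plan states .08/.08 and .81/.90. With 5,000 simulations the standard error at .08 is √(.08 × .92 / 5,000) = .004, so the figures agree.

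**Step 4: repeat with the one-event entry added.** At .05, the probability of at least one event in the first two patients is 1 − 0.95² = .0975. Otherwise (probability .9025) at least two events are needed among patients 3-8, with probability .0328. Suspension by patient 8 is .0975 + .9025 × .0328 = .1271. Continuing gives .1389 by 15 and .1455 by 23. At .25 the first two patients contribute 1 − 0.75² = .4375.

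| True rate | By n | Stated | List, exact | Definition, exact | Difference |
|---|---|---|---|---|---|
| .05 | 15 | .08 | .072 | .139 | .067 |
| .05 | 23 | .08 | .080 | .146 | .065 |
| .25 | 15 | .81 | .805 | .835 | .030 |
| .25 | 23 | .90 | .901 | .915 | .014 |

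Differences are taken before rounding. Both recursions look after every patient and treat each outcome as known before the next patient is accrued.

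**The case against.** The strongest reply is that the list is the rule. The section opens by tying suspension to thresholds given further down, and the list is introduced as the operational form. On that reading the confidence limit is the rationale and the counts are what is applied. Every listed ratio does meet the definition, so no printed entry is false. This stands as the probable intent. It does not close the gap: the list is offered as proportions that would satisfy the criterion, which makes them examples of it and not its limits. The suspension requirement is attached to sufficient evidence, defined as any qualifying ratio.

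A reader might infer that the quoted .08 is a miscalculation, or that the trial's false-suspension rate is really almost twice what is claimed. The documents support neither. The .08 is correct for the list, and the higher figure applies only if the definition is taken to override it.

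A second reply concerns size, and it also stands. The ratio is taken over accrued patients. Section 12.1 expects 24 patients in 18-24 months, or one every 0.75 to 1 month, so the third patient would arrive about 1.5 to 2 months after the first. Treatment can last six 28-day cycles (168 days, about 5.5 months). A first event after the third accrual is 1 of 3 or more and does not meet the definition. The definition's probabilities in the table, and the .0975, are therefore upper bounds.

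Finally, an early event would not go unwatched: Sections 14 and 15 provide for serious adverse event reporting and committee review as needed. That lowers the stakes but does not say whether accrual is suspended.

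**Conclusion.** The inconsistency is real and narrow. It is a conflict of wording between a definition and its list, not an arithmetic error in either. It arises only when the first affected patient is patient 1 or 2; from a single event in three patients onward, the definition and the list agree. The probability of that situation is at most .0975 at a true rate of .05. The two readings differ in eventual suspension by at most about 6.5 points by 23 patients at .05, because some of those trials would later reach a listed threshold anyway, and by 1 to 3 points at .25. These sizes rest on the exact interval, independent patients with a constant event rate, and immediate knowledge of each outcome. The consequence is a pause in accrual for committee review; the primary endpoint and the two-stage efficacy design are unaffected. It still merits correction because it concerns a mandatory safety threshold, and nothing in the documents settles the single-event case.

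**What to change.** Reconcile the two sentences in Section 12.3.2 so that one rule governs.

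- **If the list governs:** add a clause saying that it is exhaustive and that a single affected patient does not by itself trigger suspension. The quoted .08/.08 and .81/.90 then stand.
- **If the confidence-limit definition governs:** add the entry for one affected patient in the first two or fewer, and restate the probabilities as about .14/.15 at a true rate of .05 and .84/.91 at .25. Say that these assume each outcome is known before the next accrual.

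The choice belongs to the sponsor and the monitoring committee. The first option costs one clause. The second costs one list entry, four restated figures and a somewhat higher chance of an early pause when the true rate is low. Neither changes the sample size or the efficacy analysis.

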13.0 CORRELATIVE STUDIES

13.1 Assessment of CD19 and CD20 expression changes following CFZ therapy (all patients):

Bortezomib modulates CD20 expression, and affects CDC, in a time- and concentration-dependent manner.^{25, 26} Increased CD20 expression is observed in bortezomib-resistant

cells, which in turn display increased sensitivity to rituximab-mediated complement-dependent cytotoxicity. Furthermore, rituximab resistance appears to depend partly on CD20 down-expression.²⁷⁻³⁰

Therefore, we hypothesize that 1) rituximab-resistant patients will have lower CD20 expression at baseline, and 2) that CFZ may increase CD20 expression after 2 cycles. We will explore, albeit with small sample size of WM patients, whether response to subsequent rituximab in initial CFZ nonresponders is associated with CD20 expression. We postulate that overall, it may be possible to increase CD20 expression to prime tumor cells for optimal rituximab effect, with implications for sequencing these therapies.

Methods: Peripheral blood samples from each patient before therapy and again after 2 cycles of CFZ (see Study Calendar, Section 10.0), will be submitted to UW for quantitative evaluation of CD19 and CD20 surface expression (measuring mean fluorescence intensity).

- 13.2 Correlating Marrow Response Using Flow Cytometry with Paraprotein Response (WM patients only): Response assessment in WM undergoes continual evolution, but still relies on magnitude of the IgM paraprotein reduction. However, discordant responses are commonly observed between paraprotein levels, node size, and marrow involvement and appear to vary based on therapy given. IgM levels have been reported to decrease rapidly with proteasome inhibitors, transiently flare following rituximab, and lag behind marrow responses after fludarabine; best paraprotein response may be delayed, occurring months following therapy.^{22, 31, 32} Flow cytometry is particularly suited for quantifying the lymphoid cells in the marrow of WM patients.^{33, 34} The degree of B cell lymphoid involvement at end of treatment is prognostic—WM patients with less than 5% clonal B cells as in marrow samples by flow cytometry have superior outcomes.³⁵

Methods: Marrow samples from WM patients will be evaluated before treatment, after cycle 2, and at the end of study for patients with CR for flow cytometric evaluation of both lymphoid and plasma cell components, and reported descriptively alongside paraprotein responses.

- 13.3. Specimen Requirements: Submission for flow cytometry
- A 5-10 mL specimen of peripheral blood or BM aspirate in a lavender- (EDTA) or green- (sodium heparin) tube is acceptable for each draw.
 - Storage/Transport Temperature: Specimens can be transported with a cold pack or wet ice, but do not fix or freeze specimens.
 - If no significant amount of bone marrow aspirate is obtained, a fresh bone marrow biopsy **in RPMI** (cell culture medium) may be submitted for flow cytometry.
 - Formalin-fixed bone marrow biopsies or clots should be submitted for morphological evaluation and immunohistochemical studies, but they cannot be used for flow cytometry immunophenotyping.
 - Unacceptable Conditions: Frozen specimens, specimens greater than 48 hours old, specimens fixed in formalin for flow cytometry

- 13.4 Specimen Shipping Address
Attn: [name], Hematopathology Lead
Seattle Cancer Care Alliance
Hematopathology Laboratory G7800
[name]
[name]

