3.0 DRUG INFORMATION: Carfilzomib (CFZ) and Rituximab

3.1 CFZ is a synthetic small molecule peptide bearing the chemical name (2S)-N-((S)-1-((S)-4-methyl-1-((R)-2-methyloxiran-2-yl)-1-oxopentan-2-ylcarbonyl)-2-phenylethyl)-2-((S)-2-(2-morpholinoacetamido)-4-phenylbutanamido)-4-methylpentanamide. The molecular formula is C₄₀H₅₇N₅O₇ and the molecular weight is 719.91. It specifically functions as an inhibitor of the chymotrypsin-like activity of the 20S proteasome which leads to the accumulation of protein substrates within the cell and induction of apoptosis.

3.1.1 FORMULATION: Carfilzomib for Injection will be provided as a lyophilized powder which, when reconstituted, contains 2 mg/mL isotonic solution of CFZ Free Base in 10 mM sodium citrate buffer (pH 3.5) containing 10% (w/v) sulfobutylether- β -cyclodextrin (SBE β CD, Captisol®).

3.1.2 STORAGE Lyophilized Carfilzomib for Injection must be stored at 2–8°C in a securely locked area to which access is limited to appropriate study personnel. Additional drug information, in particular the Identified Risks of Carfilzomib, is contained in Appendix 20.1. Further information can be found in the product labelling.

3.2 Rituximab is a monoclonal antibody directed against the CD20 antigen on B-lymphocytes, approved for treatment of CD20-positive Non-Hodgkin Lymphomas (NHL). Rituximab will be obtained from a commercial source.

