5.0 ELIGIBILITY CRITERIA

Patients with Waldenström Macroglobulinemia or Marginal Zone lymphoma who meet inclusion/exclusion criteria below are eligible.

At least 5 patients with rituximab-refractory disease will be enrolled (best response of stable disease or progression while on treatment with, or progression within 6 months of, rituximab-containing therapy). Accrual will be modified to ensure 5 rituximab-refractory patients are enrolled, without enrolling more than 24 total patients.

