5.1 Inclusion Criteria

- Waldenström's macroglobulinemia (WM) or marginal zone lymphoma (MZL) based on institutional pathology review; see Appendix 20.3 for WM criteria. Patients may have either previously untreated or relapsed/refractory disease.
- Measurable disease: for WM presence of monoclonal IgM immunoglobulin concentration on serum electrophoresis, with lymphoplasmacytic marrow infiltrate; for MZL: measurable nodal disease measuring at least 1.5 cm in longest dimension, or splenomegaly.

- Indication for initiation of therapy, as defined in protocol section 5.3
- Age greater than or equal to 18 years old
- Adequate hematopoiesis, including ANC >1,000/ μ L and platelet count >75,000/ μ L unless disease-related (due to marrow infiltration or splenomegaly).
- Serum creatinine <2.5 mg/dL or creatinine clearance >30 cc/min.
- Bilirubin <2 x ULN and AST and ALT <3 x ULN.
- All patients must be informed of the investigational nature of this study and have given written consent in accordance with institutional and federal guidelines.
- Expected survival of >90 days.
- Females of childbearing potential (FCBP) must agree to pregnancy testing and to practice contraception.
- Male subjects must agree to practice contraception.

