9.1 Prohibited Concomitant Therapy

- The administration of concurrent medications intended to treat WM or MZL are not allowed during protocol therapy, except plasmapheresis when clinically indicated. Concurrent radiation therapy is prohibited.
- Topical and inhaled corticosteroids to treat other medical conditions are allowed. Intermittent oral or IV corticosteroid administration is allowed as premedication prior to rituximab therapy or carfilzomib in cycle 1 or future cycles if clinically indicated; for management of nausea or vomiting; or for treatment of infusion reactions.

9.2 Patients should be strongly discouraged from taking any "alternative" or "naturopathic" medications since these agents may interact with CFZ. Any use of these medications should be at the judgment of the treating physician and should be documented in the patient's medical record

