12.0 STATISTICAL CONSIDERATIONS

12.1 Accrual: We anticipate accrual of 24 patients over 18 - 24 months. Accrual will be limited to the first 9 patients initially then paused -- if needed-- to ensure the stopping rule (section 12.2 and 12.3) has not been reached before additional patients are accrued.

12.2 Sample Size: This is a Simon 2 stage (minimax) design with stopping for futility. The primary endpoint is overall response rate, measured after 2 cycles of therapy. This model requires 24 total patients to be assessable after 2 cycles.

The null hypothesis, that the true response rate of single agent CFZ is 25%, will be tested against a one-sided alternative. In the first stage, 9 subjects will be enrolled. If two or fewer patients responds, the study will be stopped for futility. If 3 or more respond, a total of 15 more subjects will be enrolled. The null hypothesis will be rejected if 10 or more responses are observed in 24 assessable subjects. This design yields a type I error rate of .05, and a power of 80%, when the true response rate after 6 cycles of CFZ is 50%.

Descriptive statistics will be used for baseline characteristics, and responses to treatment. Changes in mean fluorescence intensity pre- and post-CFZ of both CD20 and CD19 will be assessed compared using paired T testing.

Estimate time to best response, time to progression, and survival outcomes for subjects using Kaplan-Meier analysis.

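### The paired CD20 analysis ignores earlier rituximab, so clearance of residual drug could look like a carfilzomib-induced rise in CD20 if the staining antibody competes with rituximab

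*Combined protocol and SAP*

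**What the plan says.** Section 13.1 sets out the hypotheses: "we hypothesize that 1) rituximab-resistant patients will have lower CD20 expression at baseline, and 2) that CFZ may increase CD20 expression after 2 cycles". Peripheral blood taken before therapy and again after two cycles goes for "quantitative evaluation of CD19 and CD20 surface expression (measuring mean fluorescence intensity"). The only test written for these data is in section 12.2: "Changes in mean fluorescence intensity pre- and post-CFZ of both CD20 and CD19 will be assessed compared using paired T testing". It does not mention earlier rituximab. No test is specified for the first hypothesis, the baseline comparison.

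The other relevant passages are:

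- Section 3.2: "Rituximab is a monoclonal antibody directed against the CD20 antigen on B-lymphocytes".
- Section 5.0: "At least 5 patients with rituximab-refractory disease will be enrolled", refractory meaning "best response of stable disease or progression while on treatment with, or progression within 6 months of, rituximab-containing therapy".
- Section 5.1: "Patients may have either previously untreated or relapsed/refractory disease". Neither 5.1 nor 5.2 sets a minimum interval since the last rituximab.
- Section 9.1: "The administration of concurrent medications intended to treat WM or MZL are not allowed during protocol therapy". This applies once protocol therapy has begun, so it is not a washout.
- Sections 10 and 13.3 name no staining antibody and provide for no rituximab level or check for bound drug.

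**The concern.** The drug some patients received before entry and the marker being measured share a target. Rituximab still on the cell surface could keep a competing stain from binding, so the assay would read unoccupied CD20 rather than total CD20. The reading would then be low at baseline and would recover as the drug cleared during cycles 1 and 2. That recovery has the direction of the second hypothesis. A low baseline in recently treated, rituximab-resistant patients would have the direction of the first.

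The trial has no control group in which such a drift would show up. Section 13.1 hopes the CD20 results will inform the sequencing of carfilzomib and rituximab. What is at stake is how a positive CD20 finding would be read.

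**Working it through.** The plan gives no sample size, variance or effect size for CD20, so there is no planned figure to reproduce.

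**1. Time between samples.** Pre-entry laboratory studies fall within 14 days before cycle 1 (section 10). The second sample is taken after the cycle 2 day 15 dose, 28 + 14 = 42 days after cycle 1 day 1, and no later than cycle 3 day 1, which is day 56 on the same count. The gap is therefore 42 to 70 days (42 + 0 to 56 + 14), ignoring visit windows and dose delays. On-study rituximab starts on cycle 3 day 1 (section 7.2), so any masking comes from earlier treatment.

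**2. False rise in one masked patient.** Let b be the share of CD20 blocked at baseline, t the rituximab half-life and d the days between samples. Assume that blocking falls in proportion to drug. The remaining fraction is r = 2^(−d/t). With no true change,

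measured rise = (1 − b·r)/(1 − b) − 1 = b(1 − r)/(1 − b).

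Neither b nor t is in the documents. I assume t = 14 to 30 days and b = 10 to 30%. For d = 56:

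| b | t = 14 days (r = 6.2%) | t = 30 days (r = 27.4%) |
|---|---|---|
| 10% | 10.4% | 8.1% |
| 20% | 23.4% | 18.1% |
| 30% | 40.2% | 31.1% |

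Over the full 42 to 70 days, r runs from 2^(−70/14) = 3.1% to 2^(−42/30) = 37.9%. The rise then runs from 0.10 × 0.621/0.90 = 6.9% to 0.30 × 0.969/0.70 = 41.5%.

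**3. Average over the paired set.** If 5 of 24 patients are masked and all have similar true CD20, the mean false rise is 5/24 × 8.1% = 1.7% to 5/24 × 40.2% = 8.4%.

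**4. Effect on the planned test.** I simulated the paired t-test on log fluorescence with no true change, d = 56, the same b and t, and an assumed SD of the log difference of 0.2 to 0.5. The nominal chance of a significant rise is 2.5%.

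| Masked / pairs | Chance of a significant false rise |
|---|---|
| 2 / 24 | 3.0 to 6.9% |
| 5 / 24 | 3.6 to 23% |
| 5 / 12 | 3.9 to 36% |

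The 12-pair row is there because the number of pairs is uncertain. Footnote 5 of the section 10 calendar requires post-cycle-2 flow cytometry in WM patients only, whereas section 13.1 covers all patients.

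Heavier masking gives more. With 5 of 24 patients half masked at baseline (unmasked share rising from 0.50 to 0.87), the false-rise rate is 14 to 39%.

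**5. Baseline comparison.** A masked patient reads low by b itself, so by 10 to 30% under these assumptions.

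**6. When exposure is remote.** At 180 days after a dose, r is at most 2^(−180/30) = 1.6%, so little drug is left to mask CD20.

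**The case against.** The strongest reply is that the mechanism is conditional and unproven here. It needs recent rituximab, drug still bound and a stain that competes with it. The documents give no staining antibody, half-life or occupancy. If the laboratory uses a non-competing reagent, the concern largely goes away. This stands, and it limits the point to a possible bias.

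Refractory does not mean recently treated. The section 5.0 definition rests on best response or on the interval from rituximab to progression, and it sets no limit on the time from last dose to enrolment. A patient refractory years ago qualifies and would not be masked. Recently treated patients who are not refractory are also eligible, and masking in them would blur the baseline contrast. Section 13.1 says resistant and section 5.0 says refractory, and the two terms are never tied together. All of this stands.

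A reader might infer that two planned tests are biased. Section 12.2 plans only the paired one; the baseline hypothesis has no stated test. A reader might also infer that the trial will settle treatment sequencing on these data. Section 13.1 calls the work exploratory with a small sample and only postulates a sequencing benefit. Rituximab is assigned on SPEP or imaging (section 7.2), not on CD20.

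Finally, CD19 is measured in parallel and might seem to be a built-in check. It is not one by itself, since a rise in CD20 with flat CD19 is what both masking and a true CD20-specific effect would produce.

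None of this removes the gap. The planned paired test cannot tell clearance of earlier rituximab from an effect of carfilzomib, and the treatment history could help to separate them.

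**Conclusion.** The point holds as a conditional one. With no washout, a surface CD20 readout and an analysis that ignores earlier rituximab, clearance of residual drug could mimic the hypothesised rise. The same masking could contribute to low baseline CD20 in rituximab-resistant patients.

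Under the assumptions above, the effect on the planned test runs from negligible to material. The larger per-patient figure should not be read as the bias in the test, because it is diluted by unmasked patients. All of it rests on an assumed half-life, blocked share and number of masked patients, and on a competing stain.

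The documents do not support saying that the CD20 results are biased, or that the refractory group as a whole is masked. The primary response endpoint, the two-stage rule, the safety rules and treatment assignment are unaffected. This is an inexpensive improvement to an exploratory analysis.

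**What to change.** In sections 12.2 and 13.1:

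- Use the date of last rituximab from the treatment history.
- Report the paired CD20 change in all patients. As a prespecified analysis, also report it in patients never exposed to rituximab or last dosed more than 6 months before the baseline sample, with recently exposed patients shown separately. Describe the 6 months as a chosen cut-off. It is not the section 5.0 window, which runs from rituximab to progression.
- Attribute a CD20 rise to carfilzomib only if it is also seen in the never-exposed or remote group.
- For the first hypothesis, show baseline CD20 descriptively by time since last rituximab. Excluding recent patients could nearly empty a group of which only 5 are guaranteed.
- Show CD19 alongside, without treating it as proof for or against masking.

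If the laboratory's CD20 reagent does not compete with rituximab, saying so in section 13.1 would largely answer the concern.

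The cost is a few lines of wording and fewer pairs in the restricted analysis. Medical history is already taken at entry, and applying the refractory definition already calls for rituximab timing. No new samples or visits are needed.
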